7.2.2. Summary Measure

Mean treatment difference or odds ratio by visit, or hazard ratio for double blind period.

No treatment comparison for open label period.

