7.2.4. Strategy for Intercurrent (Post-Randomization) Events

For binary data, DO=NR rule will be applied to missing data until 12 weeks after 1st treatment. For time to event data, missing data will be treated as censor. All missing data for other secondary endpoints not mentioned above are treated as missing, will not be imputed, unless otherwise specified.

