
TBS (treatment benefit scale) consists of 4 answers to 1 questions “Please complete the following question by considering your current condition (urinary problems, urinary incontinence) compared to your condition before you received any study treatment in this trial”. Subjects will select their answer to this question considering their condition. Available answers are below and will be coded 1 to 4 in order to use statistical analysis.
 
 • 1 - Greatly improved • 2 - Improved • 3 - Not changed • 4 - Worsened 
The answers of 1 – Greatly improved or 2 – Improved will be regarded as positive response.
 
Other answers including missing data will be regarded as NO positive response.

Urodynamics
Urodynamics Data Convention for No IDC occurred

To take into account that there will be subjects post-treatment in whom an involuntary detrusor contraction was confirmed as not occurring during urodynamics, the data will be analysed below.
 
 • Maximum detrusor pressure during the first IDC ($P_{\max IDC}$) A value will not be imputed for subjects with no IDC since MDP during first IDC cannot be evaluated. • Volume at first IDC ($V_{P_{\max IDC}}$) A value will be imputed by MCC for subjects with no IDC.

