Efficacy: Tables						
No.	Population	IDSL / TST ID / Example Shell	Title	Programming Notes	Report at Interim	Report at Final
2.20.	FAS3	PSY1	Summary of Average Volume Voided Per Void (FAS3): TC3			Y
2.21.	FAS3	PSY2	Summary of Change from Baseline in Average Volume Voided Per Void (FAS3): TC3			Y
2.22.	FAS3	PSY2	Summary of Percent Change from Baseline in Average Volume Voided Per Void (FAS3): TC3			Y
Daily Average Number of Voids						
2.23.	FAS1	PSY1	Summary of Daily Average Number of Voids (FAS1): TC1		Y	Y
2.24.	FAS1	PSY2	Summary of Change from Baseline in Daily Average Number of Voids (FAS1): TC1		Y	Y
2.25.	FAS1	PSY2	Summary of Percent Change from Baseline in Daily Average Number of Voids (FAS1): TC1		Y	Y
2.26.	FAS1	PSY4	Summary of MMRM analysis for Change from Baseline in Daily Average Number of Voids (FAS1)		Y	
2.27.	FAS1	PSY3	Summary of ANCOVA for Change from Baseline in Daily Average Number of Voids (FAS1)		Y	Y
2.28.	FAS2	PSY1	Summary of Daily Average Number of Voids (FAS2): TC2			Y
2.29.	FAS2	PSY2	Summary of Change from Baseline in Daily Average Number of Voids (FAS2): TC2			Y
2.30.	FAS2	PSY2	Summary of Percent Change from Baseline in Daily Average Number of Voids (FAS2): TC2			Y
2.31.	FAS3	PSY1	Summary of Daily Average Number of Voids (FAS3): TC3			Y
2.32.	FAS3	PSY2	Summary of Change from Baseline in Daily Average Number of Voids (FAS3): TC3			Y

CONFIDENTIAL

204948

Efficacy: Tables						
No.	Population	IDSL / TST ID / Example Shell	Title	Programming Notes	Report at Interim	Report at Final
2.33.	FAS3	PSY2	Summary of Percent Change from Baseline in Daily Average Number of Voids (FAS3): TC3			Y
Maximum Cystometric Capacity						
2.34.	FAS1	PSY1	Summary of Maximum Cystometric Capacity (FAS1)		Y	
2.35.	FAS1	PSY2	Summary of Change from Baseline in Maximum Cystometric Capacity (FAS1)		Y	
2.36.	FAS1	PSY3	Summary of ANCOVA for Change from Baseline in Maximum Cystometric Capacity (FAS1)		Y	
Maximum Detrusor Pressure during the first Involuntary Detrusor Contraction						
2.37.	FAS1	PSY1	Summary of Maximum Detrusor Pressure during the first Involuntary Detrusor Contraction (FAS1)		Y	
2.38.	FAS1	PSY2	Summary of Change from Baseline in Maximum Detrusor Pressure during the first Involuntary Detrusor Contraction (FAS1)		Y	
2.39.	FAS1	PSY3	Summary of ANCOVA for Change from Baseline in Maximum Detrusor Pressure during the first Involuntary Detrusor Contraction (FAS1)		Y	
Volume at first Involuntary Detrusor Contraction						

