2.40.	FAS1	PSY1	Summary of Volume at first Involuntary Detrusor Contraction (FAS1)		Y	
2.41.	FAS1	PSY2	Summary of Change from Baseline in Volume at first Involuntary Detrusor Contraction (FAS1)		Y	

CONFIDENTIAL

204948

Efficacy: Tables						
No.	Population	IDSL / TST ID / Example Shell	Title	Programming Notes	Report at Interim	Report at Final
2.42.	FAS1	PSY3	Summary of ANCOVA for Change from Baseline in Volume at first Involuntary Detrusor Contraction (FAS1)		Y	
Maximum Detrusor Pressure during the Storage Phase						
2.43.	FAS1	PSY1	Summary of Maximum Detrusor pressure during the Storage Phase (FAS1)		Y	
2.44.	FAS1	PSY2	Summary of Change from Baseline in Maximum Detrusor pressure during the Storage Phase (FAS1)		Y	
2.45.	FAS1	PSY3	Summary of ANCOVA for Change from Baseline in Maximum Detrusor pressure during the Storage Phase (FAS1)		Y	
Urodynamics (Involuntary Detrusor Contraction)						
2.46.	FAS1	PSY5	Number of Subjects without an IDC (FAS1)		Y	
KHQ Domain Score						
2.47.	FAS1	PSY1	Summary of KHQ Domain Score (FAS1): TC1		Y	Y
2.48.	FAS1	PSY2	Summary of Change from Baseline in KHQ Domain Score (FAS1): TC1		Y	Y
2.49.	FAS1	PSY3	Summary of ANCOVA for Change from Baseline in KHQ Domain Score – Role Limitations and Social Limitations (FAS1)	ANCOVA will be done for only Role Limitations and Social Limitations	Y	Y
2.50.	FAS2	PSY1	Summary of KHQ Domain Score (FAS2): TC2			Y
2.51.	FAS2	PSY2	Summary of Change from Baseline in KHQ Domain Score (FAS2): TC2			Y

CONFIDENTIAL

204948

Efficacy: Tables						
No.	Population	IDSL / TST ID / Example Shell	Title	Programming Notes	Report at Interim	Report at Final
2.52.	FAS3	PSY1	Summary of KHQ Domain Score (FAS3): TC3			Y
2.53.	FAS3	PSY2	Summary of Change from Baseline in KHQ Domain Score (FAS3): TC3			Y
Proportion of Subjects attaining 100%, ≥75% and ≥50% Reduction from Baseline in the Daily Average of Urinary Incontinence Episodes						
2.54.	FAS1	PSY5	Number and Percentage of Subjects Attaining 100%, ≥75% and ≥50% Reduction from Baseline in the Daily Average of Urinary Incontinence Episodes (FAS1): TC1		Y	Y
2.55.	FAS2	PSY5	Number and Percentage of Subjects Attaining 100%, ≥75% and ≥50% Reduction from Baseline in the Daily Average of Urinary Incontinence Episodes (FAS2): TC2			Y
2.56.	FAS3	PSY5	Number and Percentage of Subjects Attaining 100%, ≥75% and ≥50% Reduction from Baseline in the Daily Average of Urinary Incontinence Episodes (FAS3): TC3			Y
Proportion of Subjects with Positive Response on the TBS						

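### The Week 6 PmaxIDC comparison keeps only subjects who still have an involuntary contraction, and no effect estimate or confidence interval is planned for losing it

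*SAP*

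**What the plan says.** - Protocol 5.1, criterion 3, requires an IDC on urodynamics before randomization. Absence of an IDC at Week 6 is therefore always a change that follows randomization.
- Protocol 9.4.2 plans an ANCOVA of change in PmaxIDC and gives no rule for a subject without an IDC. SAP 7.2.5.1 keeps the ANCOVA at Week 6, with treatment and baseline as terms.
- SAP 11.6.3 supplies the rule and expects it to be needed. For PmaxIDC: "A value will not be imputed for subjects with no IDC since MDP during first IDC cannot be evaluated". For the volume at first IDC (VPmaxIDC): "A value will be imputed by MCC for subjects with no IDC".
- SAP 7.2.4 adds: "All missing data for other secondary endpoints not mentioned above are treated as missing, will not be imputed, unless otherwise specified". Nothing else in the plan brings the no-IDC subjects back into the PmaxIDC model.
- SAP 11.10.6 lists the model output as Table 2.39, whose title begins "Summary of ANCOVA for Change from Baseline in Maximum Detrusor Pressure during the first Involuntary Detrusor Contraction (FAS1".
- The urodynamic note that closes SAP 7.2.5.1 regards absence of an IDC as evidence of benefit and has the number of such subjects summarized at Week 6. Table 2.46 shows it, under a title that begins "Number of Subjects without an IDC (FAS1". The same note excludes statistical analysis of that number.

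**The concern.** A subject whose IDC disappears has, by the SAP's own account, responded well. That subject then has no Week 6 PmaxIDC value and drops out of the ANCOVA. If the arms lose IDCs at different rates, the model compares two groups selected by response, and randomization no longer protects the contrast. The adjusted difference and its 95% CI answer a narrower question: how pressures differ between arms among subjects who still have an IDC.

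Such a conditional result can be read safely if the selecting response is estimated beside it. Here that response gets a count only. At stake is how one secondary urodynamic result is interpreted. The primary endpoint, maximum cystometric capacity (MCC) and the maximum detrusor pressure during storage (PdetMax) carry no such exclusion, and VPmaxIDC keeps the no-IDC subjects through the MCC value.

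**Working it through.** The plan gives no figure for PmaxIDC or for IDC absence, so there is none to reproduce. From the documents come 15 subjects per arm (Protocol 9.2.1) and the rules above. The no-IDC rates, SDs and correlation below are assumptions.

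**1. Who stays in the model.** Subjects left = 15 × (1 − no-IDC rate), if all are tested.
- Placebo, 10% to 20% without an IDC: 15 × 0.90 = 13.5 to 15 × 0.80 = 12.
- Active, 30% to 60%: 15 × 0.70 = 10.5 to 15 × 0.40 = 6.
- At 6 versus 12, the standard error of the difference rises by √(1/6 + 1/12) / √(2/15) = 0.500 / 0.365 = 1.37.

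**2. What selection alone can do.** Suppose the drug changes no pressure in anyone who keeps an IDC. Take SD 25 cmH2O, a baseline correlation of 0.5, and no IDC in 20% (placebo) and 60% (active). If the weakest contractions are the ones lost, the mean of those remaining rises by 0.350 SD on placebo and 0.966 SD on active. The unadjusted difference is then (0.966 − 0.350) × 25 = +15.4. Simulation with about 500,000 subjects per arm, fitting treatment and baseline, gives these adjusted differences:

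| Which contractions are lost | Adjusted difference (cmH2O) |
|---|---|
| Weakest | +13.2 |
| At random | 0.0 |
| Strongest | −13.2 |

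Over SD 20 to 30 and rate pairs from 10%/30% to 20%/60%, the two extremes run from about ±2.5 to about ±19.3. Selection alone can produce a difference of either sign.

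**3. A model in which the effect is understated.** Let the drug lower a latent pressure in everyone, and let contractions below a fixed threshold vanish (10% absent on placebo). A true shift of −0.50 SD appears as −0.32 among subjects with an IDC (22% absent on active), a loss of 1 − 0.32/0.50 = 36%. A shift of −1.00 SD appears as −0.57 (39% absent), a loss of 43%. This holds only under that model.

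**4. What an odds ratio for no IDC would look like.** For a/15 on active and b/15 on placebo, OR = a(15 − b) / [(15 − a)b].
- 9/15 versus 3/15: (9 × 12) / (6 × 3) = 6.0. The Wald SE of the log OR is √(1/9 + 1/6 + 1/3 + 1/12) = 0.833, giving 1.2 to 30.7. The exact conditional interval is 0.9 to 44.9.
- 5/15 versus 2/15: (5 × 13) / (10 × 2) = 3.25, exact 0.4 to 39.4.
- With 0/15 on placebo only a lower limit exists: 3.3 for 9/15 and 1.07 for 5/15. The chance of 0/15 is 0.95^15 = 46%, 0.90^15 = 21% or 0.80^15 = 3.5% at placebo rates of 5%, 10% or 20%.

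In the first example Wald excludes 1 and exact does not, so the method should be fixed in advance rather than chosen once the counts are known.

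**The case against.** The SAP saw the issue and dealt with it openly. PmaxIDC is undefined without an IDC, so it is not imputed. VPmaxIDC has a sensible substitute and is imputed. The no-IDC subjects are counted separately because their outcome is favourable. Absence of an IDC is not a listed endpoint in either document, the study tests no formal hypotheses (Protocol 9.1, SAP 2.4), and the sample size rests on feasibility. On that view a count is proportionate.

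Most of this stands. The non-imputation should stay, and the weight is small. But the SAP still plans point estimates with 95% CIs for its efficacy comparisons, including odds ratios for the listed binary endpoints. One more fits that approach, and it concerns the response that decides who enters Table 2.39.

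Four stronger readings are tempting and are not supported:
- **That the SAP contradicts itself.** SAP 7.2.2 names "Mean treatment difference or odds ratio by visit, or hazard ratio for double blind period", but this is a general list; it includes a hazard ratio although 7.2.5.1 fits no time-to-event model. It does not oblige an odds ratio for an unlisted outcome. This is a gap.
- **That nothing about IDC absence by arm will be seen.** Table 2.46 gives a count. If it is shown by arm, a reader can work out a crude difference. What is missing is a planned effect estimate with an interval.
- **That Table 2.39 is mislabelled because Table 2.42, titled "Summary of ANCOVA for Change from Baseline in Volume at first Involuntary Detrusor Contraction (FAS1" and so on, keeps the no-IDC subjects under the same population label.** The label names the source population. The table shells are separate documents (SAP 11.10.2 and 11.11), so missing footnotes or counts cannot be inferred from titles.
- **That the drug effect on PmaxIDC will be understated.** This is plausible under the model in step 3 of the working, but step 2 shows that the direction depends on which subjects lose their IDC.

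**Conclusion.** The point holds as a minor one. By the SAP's own rules, the Week 6 PmaxIDC ANCOVA compares arms only among subjects who still have an IDC. Its difference is conditional on a post-randomization response, and that response has no planned effect estimate or CI. This follows from the text and needs no assumption.

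The size and direction of any distortion cannot be fixed from the documents, because they give no no-IDC rates or pressures. The ±13.2 cmH2O and the wider range are illustrations from an extreme selection model with assumed rates and SDs. If few subjects lose their IDC, or both arms lose it at similar rates in similar subjects, the effect will be small. One secondary endpoint is affected.

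**What to change.** 1. In the closing note of SAP 7.2.5.1, replace the exclusion of statistical analysis with a between-arm estimate in Table 2.46: the proportion with confirmed no IDC at Week 6 by arm, among subjects with a completed Week 6 urodynamic test, with an odds ratio and an exact 95% CI in all cases.
2. SAP 7.2.4 says "For binary data, DO=NR rule will be applied to missing data until 12 weeks after 1st treatment". State that this rule is not applied here, so that an untested subject is not counted as still having an IDC.
3. Keep the PmaxIDC ANCOVA. Footnote Table 2.39 to say that it covers subjects with an IDC at Week 6, give n per arm, and state that it is descriptive and read together with Table 2.46.

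The cost is some SAP wording, one footnote and one odds ratio, all from data already collected. There are two downsides. The interval will be wide at 15 per arm (0.9 to 44.9 for 9/15 versus 3/15) and one-sided if a cell is zero. The plan will also hold one binary outcome outside its usual missing-data rule.

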11.6.4. Safety

Adverse Events
AE'S OF Special Interest
Adverse events of special interest are classified as follows, and how they will be identified are tabulated below: 
 • Urinary tract infections • Urinary retention • Residual urine volume • Possible Distant Spread of Toxin • Hypersensitivity • Potential risk of pyelonephritis

AEs of Special Interest	Preferred Term
Urinary tract infections	Urinary tract infection; Urinary tract infection bacterial; Urinary tract infection pseudomonal;
Urinary retention	Urinary retention
Residual urine volume increased	Residual urine volume increased
Hypersensitivity	Drug eruption; Dermatitis allergic; Angioedema; Stevens-Johnson syndrome; Toxic epidermal necrolysis; Drug hypersensitivity; Hypersensitivity; Anaphylactic reaction; Anaphylactic shock; Anaphylactoid reaction; Anaphylactoid shock;
Potential risk of pyelonephritis	Bacterial pyelonephritis; Pyelonephritis; Pyelonephritis acute;

As for Possible Distant Spread of Toxin, following SOC and PT terms will be used.

System Organ Class	Preferred Term
Cardiac Disorders	Bradycardia
Eye Disorders	Accommodation disorder Diplopia Extraocular muscles paresis Eyelid function disorder

	Eyelid ptosis Pupillary reflex impaired Vision blurred
Gastrointestinal Disorders	Constipation Dry mouth Dysphagia Ileus paralytic
Infections and Infestations	Botulism
Musculoskeletal and Connective Tissue Disorders	Muscular weakness
Nervous System Disorders	Bulbar palsy Cranial nerve palsies multiple Cranial nerve paralysis Dysarthria Facial paralysis Facial paresis Hyporeflexia Hypotonia Paralysis Paresis cranial nerve Peripheral paralysis Peripheral nerve palsy Speech disorder Vocal cord paralysis Vocal cord paresis
Renal and Urinary Disorders	Urinary retention [1]
Reproductive System and Breast Disorders	Pelvic floor muscle weakness
Respiratory, Thoracic and Mediastinal Disorders	Aspiration Diaphragmatic paralysis Dysphonia Dyspnoea Pneumonia aspiration Respiratory arrest Respiratory depression Respiratory failure

[1]; Note that since GSK1351880 is injected into the urinary bladder for the treatment of OAB, and urinary retention is considered an expected localized effect, the PT “urinary retention” will not be considered a Possible Distant Spread of Toxin event for this study.

Treatment Relationship	Definition
Treatment-related	Yes, If relationship in study drug-related and/or injection procedure-related is ‘Yes’ according to below definitions.
Study Drug-related	If relationship is marked ‘YES’ on Inform/CRF OR value is missing.
Injection procedure-related	If relationship is marked ‘YES’ on Inform/CRF OR value is missing.

NOTES:

Treatment Relationship	Definition
------------------------	------------

- If the study withdraw date is missing then the AE will be considered to be On-Treatment.

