## 4.6.1. Risk Assessment

Potential Risk of Clinical Significance	Summary of Data/Rationale for Risk	Mitigation Strategy
Investigational Product (IP) : GSK1358820		
Urinary tract infections (UTI)	
As the result of integrated data with 2 completed phase 2 studies (Studies 191622-511 and 191622-518), 2 completed pivotal phase3 studies (Studies 191622-515 and 191622-516) and an interim cut of the long-term extension study (Study 191622-094), the frequency of UTI as an adverse event on first treatment that patients received occurred in 53.2% of patients in the 300 U BOTOX group, 49.2% of patients in the BOTOX 200U group and 35.7% in the placebo group (refer to IB section 5.2.4.1 Neurogenic Detrusor Overactivity). The following potential factors that may have facilitated the occurrence of UTI were:
 
 
1) Routine, daily scheduled CIC for bladder emptying purposes – both in patients who were already catheterizing and those patients in whom catheterization (clean, intermittent) was initiated to manage emptying the bladder when urinary retention occurred.
 
2) Elevated PVR urine volume in patients who did not use catheterization pre- or post-treatment
 
3) Cystoscopy for study drug administration procedure (intradetrusor injection) and urodynamic evaluations for efficacy assessments during study participation.
 
	
Patients with potential risk for these events will be excluded from this study to reduce the risk of UTI (refer to Protocol section 5.2 exclusion criteria 13、 14、 18 and 21)
 
Urinalysis, urine culture and sensitivity test will be performed at each visits. If bacterial infection is confirmed, treatment with antibiotics will be administered in the opinion of the investigators/subinvestigators. The patients are not allowed to receive the injection of the investigational product,if the patient is symptomatic for UTI (refer to Protocol section 7.4.6.2.Urinalysis).
 
Treatment with antibiotics will be administered to prevent bacterial infection before / after the injection of the investigational product (refer to Protocol section 6.1.2.1.Antibiotics)

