Urinary retention	
As the result of integrated data with 2 completed phase 2 studies (Studies 191622-511 and 191622-518), 2 completed pivotal phase 3 studies (Studies 191622-515 and 191622-516) and an interim cut of the long-term extension study (Study 191622-094), the frequency of urinary retention as an adverse event on first treatment that patients received occurred in 21.3% of patients in the BOTOX 300 U group, 17.2% in the BOTOX 200U group and 2.9% of patients in the placebo group (refer to IB section 5.2.4.1 Neurogenic Detrusor Overactivity).
 
Intradetrusor injection of BOTOX causes a detrusor muscle relaxation that leads to a decrease in the contractions of the detrusor muscle. This detrusor muscle relaxation may lead to an inability of the detrusor muscle to effectively contract during voiding in some patients thus causing a residual accumulation of urine in the bladder evident as an increased PVR volume, or may manifest as a patient's inability to void due to urinary retention (IB section 5.2.5 Clinical Safety in the published literature).
	
Patients with potential risk for these events will be excluded from this study to reduce the risk of urinary retention (refer to Protocol section 5.2 exclusion criteria 18 and 21)
 
PVR urine volume will be assessed at each visit. Clean intermittent catheterization (CIC) and additional follow-up visit will be performed dependent on the PVR as well as subject's symptoms (refer to Protocol section 7.4.7. Post-void residual urine volume and Appendix 5 Management guideline of PVR).

Pyelonephritis	
In NDO clinical studies, pyelonephritis as an AE was uncommon and was reported in one patient (0.4%) in the BOTOX 300U group during placebo-controlled treatment cycle 1. However, based on the patient population who will be
	
Please refer to the mitigation strategy UTIs

	receiving instrumentation to deliver intradetrusor injections of BOTOX, and a potential temporary increase in PVR urine post treatment, mainly in the first 12 weeks, patients with bladder disorders with urinary incontinence who have a prior UTI may potentially progress from UTI to pyelonephritis.	
Other		

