#### **7.4.6.2.2. Urinalysis, Culture and Sensitivity**

Urinalysis, culture and sensitivity will be centrally performed at the central laboratory. A urine culture and sensitivity test will be performed when urinalysis results with a urine reagent strip are suggestive of a UTI (positive nitrites or leukocyte esterase) (see below for the definition of AE urinary tract infection).

If PVR at scheduled visits is  $\geq 200$  mL and an additional follow-up visit occurs 1 week later, urine culture and sensitivity test at the central laboratory will be performed (see 7.4.7 Post-void residual (PVR) urine volume).

- **Definition of AE urinary tract infection**

For non-catheterizing patients, if both of the following criteria are fulfilled, urinary tract infection is recorded as an adverse event, irrespective of symptoms:

- 1) The result of urine culture is positive (with the presence of bacteriuria with  $\geq 10^5$  CFU/mL)
- 2) Leukocyturia with  $> 5$  per high power field is noted.

For catheterizing patients, the investigator will take into account patient symptoms, presence of significant leukocyturia, urine culture results, need for antibiotic treatment, etc. A urinary tract infection will be recorded as an adverse event if in the opinion of the investigator, it is symptomatic and requires antibiotic treatment.

If subjects report urinary tract infection, which is diagnosed by a physician at a medical institution other than study sites (i.e., a family doctor or critical care physician), the results of urinalysis, urine culture, and sensitivity test should be obtained as far as possible.

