### 12.3.4. Recording of AEs and SAEs

AEs and SAE Recording:

 
• When an AE/SAE occurs, it is the responsibility of the investigator to review all documentation (e.g., hospital progress notes, laboratory, and diagnostics reports) relative to the event.
 
• The investigator will then record all relevant information regarding an AE/SAE in the CRF
 
• It is not acceptable for the investigator to send photocopies of the subject's medical records to GSK in lieu of completion of the GSK, AE/SAE CRF page.
 
• There may be instances when copies of medical records for certain cases are requested by GSK. In this instance, all subject identifiers, with the exception of the subject number, will be blinded on the copies of the medical records prior to submission of to GSK.
 
• The investigator will attempt to establish a diagnosis of the event based on signs, symptoms, and/or other clinical information. In such cases, the diagnosis will be documented as the AE/SAE and not the individual signs/symptoms.
 
• Subject-completed Value Evidence and Outcomes questionnaires and the collection of AE data are independent components of the study.
 
• Responses to each question in the Value Evidence and Outcomes questionnaire will be treated in accordance with standard scoring and statistical procedures detailed by the scale's developer.
 
• The use of a single question from a multidimensional health survey to designate a cause-effect relationship to an AE is inappropriate.
 

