8.2. Adverse Events of Special Interest Analyses

The definition of AEs of special interest and their MedDRA preferred term is described as 11.6.4. The number and percentage of subjects experiencing an AE of special interest and the total number of AEs of special interest will be summarized. Listing will also be produced.

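### The urinary tract infection special-interest category is a closed list of three preferred terms, so an infection coded to any other term is missing from the special-interest displays

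*SAP*

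**What the plan says.** SAP 8.2 takes the special-interest summaries and listing from one place: "The definition of AEs of special interest and their MedDRA preferred term is described as 11.6.4". Section 11.6.4 then names the categories and says of the events that "how they will be identified are tabulated below". The UTI row reads "Urinary tract infection; Urinary tract infection bacterial; Urinary tract infection pseudomonal". The pyelonephritis row also has three terms. For comparison, the hypersensitivity row has eleven. No row carries wording such as 'for example', a grouped query, or a step to review coded terms against the list.

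The list drives Tables 3.54 and 3.57 (treatment cycle 1), 3.60, 3.63 and 3.66 (GSK1358820 cycles 1 to 3), 3.68 (overall period) and Listing 22.

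Protocol 4.6.1 gives first-treatment UTI frequencies of "49.2% of patients in the BOTOX 200U group and 35.7% in the placebo group". The next most frequent risk quantified there is urinary retention, at "17.2% in the BOTOX 200U group and 2.9% of patients in the placebo group".

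Protocol 7.4.6.2.2 sets out when the event is recorded. For non-catheterizing patients who meet a culture and a leukocyturia criterion, "urinary tract infection is recorded as an adverse event, irrespective of symptoms". For catheterizing patients the rule rests on judgement: "A urinary tract infection will be recorded as an adverse event if in the opinion of the investigator", the infection is symptomatic and needs antibiotics. Protocol 12.3.4 adds the general rule that "the diagnosis will be documented as the AE/SAE and not the individual signs/symptoms".

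**The concern.** The special-interest tables are where a reader looks for the number of subjects with any UTI, the most frequent of the risks that protocol 4.6.1 quantifies. The list makes that number depend on how each infection was worded and coded. Its own entries show this: bacterial and pseudomonal infections stand apart from the plain term, so wording can move an infection to a different code. Only one organism is named, and there is no term for infection located in the bladder.

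The protocol leaves room for such wording:

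- A positive dipstick leads to central culture and sensitivity testing (7.4.6.2), so a site can learn the organism.
- Physicians outside the study sites may make the diagnosis (7.4.6.2.2).
- For catheterizing patients recording rests on investigator opinion. SAP 8.5.2 puts the two void patterns without intermittent catheterization at fewer than five subjects in total, so nearly all subjects probably come under that rule.

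The grouped count cannot be rebuilt from the all-event tables. One subject may have several infections under different preferred terms, so preferred-term rows cannot be added. The organ-class row can include unrelated infections.

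**Working it through.** **Is the list closed?** SAP 11.6.4 says that the events are identified by the tabulated terms, and 8.2 points only to that table. No fallback rule appears elsewhere in the SAP. The semicolon at the end of the UTI row is not a sign of a truncated list, because the hypersensitivity and pyelonephritis rows end in the same way.

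**Which displays are affected?** Tables 3.54 and 3.57 use the double-blind safety population and set 200 U against placebo. Tables 3.60, 3.63, 3.66 and 3.68 cover only time after GSK1358820, so they have no placebo comparison to distort. In these tables a missed term can only lower the reported incidence.

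**Weight of one subject.** SAP 8.1 says that with about 15 subjects per group a single subject already exceeds 5%. Check: 1/15 = 6.7%, which agrees.

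**Expected counts with a complete list.** The inputs are the 49.2% and 35.7% from protocol 4.6.1 and 15 per arm from protocol 9.2.1.

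- 200 U: 0.492 × 15 = 7.4 subjects
- Placebo: 0.357 × 15 = 5.4 subjects
- Difference: 49.2 − 35.7 = 13.5 points, about 2 subjects

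**Effect of missed terms.** Let f be the share of subjects with UTI whose infections in the period all code to unlisted terms. The documents give no value for f, so 10%, 25% and 50% are assumptions, taken as equal in both arms. The displayed count is 15 × p × (1 − f), and the displayed difference is 13.5 × (1 − f).

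| f (assumed) | 200 U shown | Placebo shown | 200 U missing | Placebo missing | Difference shown |
|---|---|---|---|---|---|
| 0 | 7.4 | 5.4 | 0 | 0 | 13.5 points |
| 10% | 6.6 | 4.8 | 0.7 | 0.5 | 12.2 points |
| 25% | 5.5 | 4.0 | 1.8 | 1.3 | 10.1 points |
| 50% | 3.7 | 2.7 | 3.7 | 2.7 | 6.8 points |

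Equal loss shrinks the difference in proportion and does not remove it.

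**The case against.** The strongest reply is that the protocol largely fixes the name of the event. Section 7.4.6.2.2 defines an adverse event called urinary tract infection. The investigator's discretion covers whether to record it, not what to call it, and nothing asks the site to name the organism. Section 12.3.4 only says to record a diagnosis in place of symptoms, which moves a symptom such as fever towards a listed term. This stands, and it is why the effect is probably small.

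The events also stay visible. Every adverse event is tabulated by organ class and preferred term, and Listings 15 to 17 show them all, including the link from verbatim text to term. In a 30-subject trial a reader could find a stray term. This stands too: the gap is confined to the special-interest displays. The study tests no formal hypothesis, so no inference turns on it.

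Three stronger readings are tempting and go beyond the documents:

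- **Every other organism is lost.** The documents give neither the MedDRA version nor its content. A named organism that codes to the bacterial term would be captured.
- **The difference could fall to one subject or none.** Removing one or two infected subjects from the active arm alone would do this, but nothing suggests that wording differs by arm during the double-blind phase. Chance alone could remove one subject more from one arm than from the other, which would move the difference by 6.7 points.
- **Six tables give a distorted arm comparison.** Only Tables 3.54 and 3.57 compare with placebo.

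The list may itself come from a blinded look at coded terms. The SAP does not say so. If it does, stating that would answer most of the point.

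**Conclusion.** The specification gap is certain: three terms, used as the operative rule, with no grouping and no review. Any urinary infection coded to another preferred term is left out of the special-interest tables and listing while remaining in the all-event displays. The same holds for the pyelonephritis row.

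The size is not known and is probably small, because the protocol's definition favours a listed term. The figures of 12.2 to 6.8 points against 13.5 illustrate an assumed equal loss of 10% to 50%. They are not estimates of what will happen. They also rest on UTI rates pooled from earlier studies whose own term set is not shown. The placebo comparison is exposed only in Tables 3.54 and 3.57; elsewhere the consequence is understated incidence.

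**What to change.** - In SAP 11.6.4, define the UTI category as all urinary tract infection preferred terms, whatever the organism, at lower or unspecified site. Give upper tract infection a matching definition in place of the three pyelonephritis terms.
- Confirm the resulting list by blinded review of all coded infection and urinary terms before the interim unblinding. The timing matters because Table 3.54 is produced only at the interim.
- Check terms that arise after the interim cut against the same definition, without reopening it.
- Footnote the included preferred terms under each special-interest table.

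The cost is SAP wording and one term review, with no new data. SAP 2.1 records a blind review already done for another endpoint, so the step is feasible. The downside is a possibly slightly higher reported UTI rate.
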